7.3.4 Issues in Sample Size Computation

It is possible that indexes or network members assigned to the experimental group will interact with those assigned to the control. This may attenuate the differences between networks and lead to an underestimation of the effect of the intervention. To take this in account, the study has been powered to detect a decrease of 40% (i.e. a relative risk of 0.6), even though in the SHIELD study, unadjusted OR in excess of 2.0 and adjusted OR as high as 3.0 were observed in behavior change. See Section 4.1 for additional information regarding the possibility of contamination.

The seroincidence rate and the average number of network members will be monitored closely during the study to assure that adequate power is attained.

7.4 Random Assignment

Individuals found eligible for participation in the study as an index will be randomized to one of the two study groups in a ratio of 1:1 along with their networks. The randomization will be stratified on study site and blocked (with random sequences of block sizes) within study site to

ensure that the assignment sequence is not predictable and yet ensure that balance between experimental and control assignments is maintained within each study site over the entire period of recruitment.

7.5 Analysis Plan

7.5.1 Primary Analysis

HIV seroincidence

Comparison of HIV seroincidence in the two arms will be based on the decrease in risk of infection between the two arms estimated via proportional hazards regression, stratified by site. Statistical estimation and inference will be based on the marginal models approach to extending the Cox model to the analysis of correlated survival data, described for example in Therneau. This has much in common with the Generalized Estimating Equation (GEE) approach of Zeger, et al.36

HIV seroincidence in Thailand

The comparison of seroincidence rates between arms will be repeated for the Thailand site alone.

7.5.2 Secondary Analysis – Behavioral

- HIV drug and sexual risk behaviors
- Psychosocial measures of network norms

Both incidence and rates of each risk behavior will be compared between arms using GEE and Mixed Linear Models (MLE). Perceived norms reported by index and network members will be analyzed using GEE, MLE and methods for repeated measurement of ordered categorical responses.³⁷

Comparisons will be made between arms for

- 1. Network aggregates overall, between sites, and within sites
- 2. In network indexes alone, overall, between sites, and within sites
- 3. Between indexes and networks overall, between sites, and within sites
- 4. Between HIV-infected and uninfected network members overall, between sites, and within sites.

Covariates adjusting for type and frequency of injected drug, alcohol use, drug treatment, and network characteristics, in addition to demographic variables, will be considered.

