Study Population:	HIV-uninfected injection drug users (index participants) and individuals identified by each index participant as members of his/her sex and/or drug using networks (network members) in Philadelphia, Pennsylvania, USA and Chiang Mai and Chiang Rai, Thailand
Study Size:	900 networks (300 in Philadelphia, 600 in Thailand) consisting of 900 index participants and approximately 1,350 HIV-uninfected network members (an average of 1.5 per index), for a total of approximately 2,250 HIV-uninfected participants. Allowing for the enrollment of HIV-infected network members and assuming an HIV prevalence of 20% in Philadelphia and 30% in Thailand, approximately 90 and 270 HIV-infected network members will be enrolled in Philadelphia and Thailand, respectively. The average network size across networks, including both HIV-positive and negative network members, is 1.9 network members per index participant, giving a total sample size of 2,610.
T., 4	To deep an ation of a contract of the second contract of the state of the state of the state of the state of the

Intervention:	Index participants will be randomized in a 1:1 ratio with their network members
	to one of two study arms as shown below

Study Arm	Behavioral Intervention					
	Index Participants Network Members					
Experimental Arm n~450 networks (450 index participants and approximately 855 network members)	Enhanced HIV counseling and testing plus Six 2-hour network oriented peer- educator sessions during weeks 1 to 4 and Booster session at months 6 and 12	Enhanced HIV counseling and testing				
Control Arm n ~450 networks (450 index participants and approximately 855 network members)	Enhanced HIV counseling and testing	Enhanced HIV counseling and testing				

Study Duration:	Approximately 48 months total. Enrollment will require approximately 30 months. Participants will be followed for a minimum of 18 months and a maximum of 30 months.					
Primary Objective:	To determine whether the peer-educator intervention reduces the rate of HIV infection among injection drug users and members of their HIV risk network					
Secondary Objectives	:					
	1. To determine whether the intervention reduces reported injection and sexual HIV risk behaviors in index participants and/or network members					
	2. To determine whether the intervention changes substance use network norms for injection and sexual HIV risk practices					

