Experimental indexes were significantly more likely than control indexes at the three-month follow-up to report reduction in drug-related HIV risk behaviors. At the 18-month follow-up, HIV-uninfected index participants in the experimental condition reported significantly less frequent needle sharing compared to those in the control condition (OR=2.83, p=0.03) and less frequent injecting of heroin and cocaine than in the control condition (OR=2.74, p=0.06). In multiple logistic regression models of HIV-uninfected participants, controls were more than twice as likely as experimental subjects to report needle and cooker sharing in the prior six months.

This study suggests that drug networks are sufficiently stable to be identified and be the focus of a clinic-based network intervention. The intervention had long-term effectiveness for modifying drug risk behaviors among HIV-uninfected individuals, and was effective for both clinic- and street-recruited participants. The intervention had limitations in that it did not appear to reduce sexual risk behaviors, nor was it effective in reducing the risk behaviors of HIV-infected participants.

The SHIELD (Self-Help In Eliminating Life-threatening Disease) study conducted in Baltimore, Maryland, USA sought to introduce health education, communication skills, and risk reduction strategies, as well as to encourage a pro-social identity among participants. The intervention emphasized the interdependence of HIV risk, protection of oneself and one's family, friends, and community, and promoted individual practice and peer advocacy of health protective behaviors as a means of mutual HIV protection. The intervention encouraged participants to introduce safer sex and drug norms to their social networks by conducting outreach education among their drug and sex network members and others in their community.

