2.2 Secondary Objectives

- 1. To determine whether the intervention reduces reported injection and sexual HIV risk behaviors in index participants and/or network members
- 2. To determine whether the intervention changes substance use network norms for injection and sexual HIV risk practices
- 3. To determine whether the intervention effects on injection and sexual HIV risk behaviors differ between index and network participants, or by HIV status in each study arm
- 4. To determine whether the intervention effect on behaviors identified as important mediators of the intervention is similar at both sites

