2.3 Study Design

This is a Phase III, multi-site, two-arm, randomized, controlled study of a network-oriented peer education training intervention for the prevention of HIV infection through reduction of HIV risk behaviors among HIV-uninfected IDUs and members of their HIV risk networks. (See study design and randomization schema on page 3.)

IDUs will be recruited using street and community outreach methods in Chiang Mai and Chiang Rai, Thailand, and Philadelphia, Pennsylvania, USA. Outreach workers will supply basic

information about the study in geographic areas and settings frequented by drug users and will encourage these individuals to seek screening at a local study site. Individuals who present at the study clinic will undergo informed consent for screening, a screening eligibility survey, and HIV counseling and testing. Individuals will be told when to return for their HIV test results, post-test counseling and further screening. Those who are HIV-uninfected, who meet preliminary eligibility requirements, and are willing to participate, will undergo informed consent for the study. These persons are referred to as **index participants** throughout the protocol. Each index participant will then be asked to identify and attempt to recruit at least two members of his/her sex and/or drug HIV risk network. One or more of the network members identified must complete all screening procedures and be determined eligible for this network to be randomized and enrolled. These HIV risk network members are referred to as network members throughout the protocol. HIV-infected and uninfected network members are eligible for enrollment. HIVinfected network members will not contribute to the primary efficacy analysis, although they will contribute to secondary endpoint analyses. Inclusion of HIV-infected network members will ensure that the networks enrolled broadly represent the IDU populations at the study sites. It will also help preserve the confidentiality of the HIV status of each participant. These network members will be offered referrals to support services as described in Section 8.4.1. Adjustments will be made to the study sample size in the event that the number of HIV-infected network members enrolled could substantially reduce the study's ability to detect an intervention effect. See Section 3.4 for details on the recruitment process.

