3.1 Inclusion Criteria

3.1.1 Index Participants

Individuals must meet all of the following criteria to be eligible for inclusion in the study as an **index participant:**

- Of legal age to independently provide written informed consent for research
- Provide written informed consent for screening and study participation
- Report having injected drugs at least 12 times in the last three months
- Been out of methadone maintenance treatment for at least 3 months and have relapsed
- HIV negative on specimen obtained within 60 days prior to randomization
- Willing to identify and attempt to recruit at least two HIV risk network members who are eligible for study participation according to the criteria in Sections 3.1.2 and 3.2.2.
- Able to recruit at least one HIV risk network member who is eligible for study participation according to the criteria in Sections 3.1.2 and 3.2.2.

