Enrolling 445 networks per arm implies a study enrollment of approximately 2,250 HIVuninfected participants: approximately 150 networks per arm in Philadelphia (750 HIVuninfected participants) and 300 networks per arm in Thailand (1500 HIV-uninfected participants). The protocol allows for the enrollment of HIV-infected network members, and assuming a prevalence of 20% and 30% amongst injectors in Philadelphia and Thailand respectively, we are projecting enrollment of 90 HIV-infected network members in Philadelphia and 270 in Thailand. The total participant enrollment, including both HIVinfected and HIV-uninfected participants, is thus projected to be 2610: 1770 in Thailand and 840 in Philadelphia, with an average of 1.9 network members per index participant. Network members who are infected with HIV will be excluded from the analysis of the primary endpoint.

For the endpoint at the Thailand site alone, assuming a higher seroincidence of 8% per year, 90% power to detect a 40% reduction in seroincidence is achieved with 332 networks per arm.

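### The planned comparison of effects in indexes and network members does not hold HIV status fixed, so part of any role difference may reflect HIV status if the intervention works less well in infected participants

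*Protocol*

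**What the plan says.** - **Objective.** Secondary objective 3 (protocol 2.2) asks whether effects on risk behavior "differ between index and network participants, or by HIV status in each study arm". These are two questions.
- **Indexes.** Section 3.1.1 requires each index to be "HIV negative on specimen obtained within 60 days prior to randomization".
- **Members.** Section 2.3 states that "HIV-infected and uninfected network members are eligible for enrollment". Infected members are left out of the primary analysis, "although they will contribute to secondary endpoint analyses".
- **Numbers.** Section 7.3.1: "we are projecting enrollment of 90 HIV-infected network members in Philadelphia and 270 in Thailand".
- **Analysis.** Section 7.5.2 lists four between-arm comparisons. Item 3 is "Between indexes and networks overall, between sites, and within sites"; read with objective 3, this is index against network participants. Item 4 compares infected with uninfected members, so it holds role fixed. The covariates to be considered in 7.5.2, and those in 7.2.4, do not include HIV status.
- **Background.** Of the earlier network trial (SAFE), section 1.1.2 says that the intervention did not appear to reduce sexual risk, "nor was it effective in reducing the risk behaviors of HIV-infected participants".

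**The concern.** Item 4 answers the HIV-status question with role held constant. Item 3 does not do the reverse: it sets a wholly uninfected group against a mixed one. If the intervention does less for infected people, the average effect in members falls below that in indexes even when trained indexes and untrained uninfected members benefit equally.

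Section 2.3 expects members to benefit indirectly through their index. A shortfall in members could therefore be taken as a sign that the benefit is not passed on, when it comes from the HIV composition of the two groups. The protocol's own background gives a reason to expect an effect that varies with HIV status.

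**Working it through.** **1. The plan's projection reproduces.** There are 300 networks in Philadelphia and 600 in Thailand, with 1.5 uninfected members each, and 7.3.1 applies 20% and 30% to the uninfected counts.
- Philadelphia: 300 × 1.5 = 450; 0.20 × 450 = 90 infected.
- Thailand: 600 × 1.5 = 900; 0.30 × 900 = 270 infected.
- Members: 1,350 + 360 = 1,710, or 1.9 per index. Total: 900 + 1,710 = 2,610, as stated.

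**2. Infected share of members (indexes: 0%).**
- Overall 360/1,710 = 21.1%; Thailand 270/1,170 = 23.1%; Philadelphia 90/540 = 16.7%.
- If 20% and 30% are instead shares of all members: 450 × 0.20/0.80 = 112.5 and 900 × 0.30/0.70 = 385.7, so 498.2/1,848.2 = 27.0% overall.

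**3. Size of the spurious difference.** Let every uninfected participant, of either role, have effect d; infected members have effect f × d and make up a share w of members. The role contrast then has expectation w(1 − f)d instead of 0.
- f = 0, d = 10 points: 0.211 × 10 = 2.1 points.
- f = 0, d = 15 points: 3.2 points.
- f = 0.5, d = 10 points: 1.05 points.
- f = 1: 0.

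The 10- and 15-point effects are those of section 7.3.2.

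**4. Standard error.** With N networks per arm, m members per index, v visits per person, within-person correlation r_w and within-network correlation r_n:

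Var = 2p(1 − p) × [ (1 + (v − 1)r_w)/(Nv) + (1 + (v − 1)r_w + (m − 1)v·r_n)/(Nmv) − 2r_n/N ]

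From the protocol: N = 450, m = 1.9. Assumed: v = 3.8 after losses (at most 5 in the protocol) and p = 0.45. The correlations are also assumptions; 0.1 to 0.3 is the range of the protocol's power tables, and 0.5 allows for stable personal behavior.

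Example, r_w = r_n = 0.2: the bracket is 1.56/1,710 + 2.244/3,249 − 0.4/450 = 0.000714. Multiplied by 0.495 this gives 0.000353, so SE = 0.0188.

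**5. Probability that a two-sided 5% test declares a role difference (21.1% infected).**

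| r_w | r_n | SE | 10 points, f = 0 | 15 points, f = 0 | 10 points, f = 0.5 |
|---|---|---|---|---|---|
| 0.1 | 0.1 | 0.0199 | 18% | 35% | 8% |
| 0.2 | 0.2 | 0.0188 | 20% | 39% | 9% |
| 0.3 | 0.3 | 0.0176 | 22% | 43% | 9% |
| 0.5 | 0.2 | 0.0269 | 12% | 22% | 7% |
| 0.5 | 0.1 | 0.0299 | 11% | 18% | 6% |

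**6. Simulation.** With five visits, 50% control prevalence, a cluster-robust variance and 1,000 runs per scenario, rejection at f = 0 was 15-22% for 10 points and 21-45% for 15. With members restricted to the uninfected it was 4-6% in every scenario.

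**7. By site (10 points, f = 0).**
- Philadelphia alone (N = 150, bias 1.7 points): 6-8% by the formula; 7-9% with five visits.
- Between sites: the biases differ by 2.31 − 1.67 = 0.64 points, or 1.0 point if the shares are 20% and 30%. Rejection is between 5% and 6%.

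**8. Cost of restriction.** Using m = 1.5 instead of 1.9 multiplies the SE by 1.045.

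**The case against.** **The items are one-line labels, and a statistical analysis plan could restrict or stratify.** It could. But 7.5.2 already names the groups to be compared, and item 4 shows that HIV status is handled at this level of detail. An analysis plan that follows item 3 as written inherits the mixture.

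**Members as enrolled are a legitimate population.** This stands in part. Section 2.3 admits infected members so that networks represent the local injecting population. If item 3 means members as enrolled, their average effect really is smaller in the scenario above, and rejection is correct. It is a false positive only when read as an effect of role, which is the reading that objective 3 invites by listing HIV status separately.

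**Item 4 would reveal the cause.** It would show the heterogeneity, but it leaves the item 3 estimate unchanged.

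**The premise rests on one earlier trial.** Fair. The manual is based on SHIELD (4.1.1), where 20% of recruited members were HIV-positive; the protocol reports serostatus-adjusted effects there and no lack of effect in infected participants. SAFE also showed no apparent effect on sexual risk, so under its pattern the sexual endpoints carry no spurious role difference.

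**Restriction does not isolate role.** True. Indexes must be frequent recent injectors (3.1.1), whereas members may qualify through sex alone (3.1.2). Restriction removes the HIV-status part only.

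**Conclusion.** The point holds as a conditional weakness of a secondary analysis. If the intervention does nothing for infected members, the overall item 3 contrast carries a spurious difference of about 2 points for a 10-point effect, and rejection is roughly 11-22% against a nominal 5% (18-43% at 15 points). With half the effect in infected members it is 6-9% at 10 points. With equal effects by HIV status there is no bias. The ranges rest on the assumed visits, prevalence and correlations.

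Three stronger readings might be inferred, and the documents do not support them:
- **Error rates of 32-40%.** These come from applying 30% infected to all 450 networks per arm. That is the Thai figure in "assuming an HIV prevalence of 20% in Philadelphia and 30% in Thailand"; the projected overall share is 21%, and 27% on the most generous reading.
- **Distorted between-site comparisons.** The biases at the two sites differ by at most about 1 point, and rejection stays between 5% and 6%.
- **A threat to the primary result.** Section 7.3.1 excludes infected members from that analysis.

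**What to change.** In 7.5.2, state that item 3 compares indexes with network members who were HIV-uninfected at screening, in its overall, between-site and within-site versions. Use screening status, which is already collected and cannot be affected by the intervention, and not status during follow-up.

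An equivalent route is to keep all members and include an arm-by-baseline-HIV-status term. HIV status as a main effect alone would not do, because the problem lies in how the intervention effect varies.

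If wanted, report the comparison with all members as enrolled alongside it, labelled as not isolating role. Infected members stay in item 4 and in the network aggregates of item 1.

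The cost is a short addition to the text and a standard error about 4-5% larger for this contrast. No new data or participants are needed. Differences in injecting criteria between the roles remain and should be named when the result is interpreted.

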7.5.3 Secondary Analysis – Behavioral Correlates

Partial behavioral surrogates will be identified using the methods referenced in Section 7.3.3. As described there, models with behavioral measures as outcomes and using site and

intervention arm as covariates will examine whether the intervention effects on behavior are similar at both sites.

7.6 Interim Monitoring Process

The duration of the study will be approximately 4 years. It is estimated that the enrollment period will be approximately 30 months. Study conduct will be monitored regularly by the HPTN Study Monitoring Committee (SMC) with a focus on issues relating to quality of study conduct, such as overall and site-specific rates of recruitment, adherence to study interventions and visit schedules, and retention. The sample size may be adjusted after 12 months if it is apparent that the mean number of HIV-uninfected network members enrolled is insufficient to achieve adequate power.

The study will also be monitored by the DSMB. Administrative data will be reviewed every 6 months during the first 18 months of the study. Primary and secondary endpoint data will be monitored annually. Sequential monitoring methods will be used to develop boundary guidelines for early termination.

The randomization code will be maintained by the research biostatistician at the HPTN Statistical and Data Management Center. At each interim efficacy analysis, the chairman of the DSMB will be given a sealed envelope with the randomization code enclosed. The DSMB will be encouraged to conduct unblinded reviews of efficacy data.

8.0 HUMAN SUBJECTS CONSIDERATIONS

8.1 Ethical Review

This protocol and the template informed consent forms contained in Appendices III through V will be reviewed and approved by the HPTN Protocol Review Committee (PRC) and DAIDS Prevention Science Review Committee (PSRC) with respect to scientific content and compliance with applicable research and human subjects regulations.

The protocol, site-specific informed consent forms, participant education and recruitment materials, and other requested documents – and any subsequent modifications – also will be reviewed and approved by the Institutional Review Boards/Ethical Committees (IRBs/ECs) bodies responsible for oversight of research conducted at the study sites.

Subsequent to initial review and approval, the responsible local IRBs/ECs will review the protocol at least annually. The investigator will make safety and progress reports to the IRBs/ECs at least annually and within three months of study termination or completion. These reports will include the total number of participants enrolled in the study, the number of participants who completed the study, all changes in the research activity, and all unanticipated problems involving risks to human subjects or others. In addition, all detailed results of DSMB reviews of the study will be provided to the IRBs/ECs.

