Index participants and network members will have follow-up visits every six months. The study duration will be approximately 48 months. Enrollment is expected to take approximately 30 months. Participants will be followed for a minimum of 18 months and a maximum of 30 months at each site. Every six months, participants will be administered surveys designed to assess the following: HIV risk behavior; network characteristics; the intensity of the intervention delivery; social harms experienced that may be associated with study participation; and intervention contamination in the control arm (i.e. sources of exposure to HIV prevention-related messages and materials). In addition, perceived network norms will be assessed annually. The behavioral risk survey will be administered prior to risk reduction counseling by an individual other than the person who administered the counseling. Behavioral risk survey interviewers will be blinded to the study arm of the participants.

To enhance retention, participants will be contacted in-between their scheduled six-month followup visits to update their locator information (e.g., address, telephone number, name and address of family members), confirm or re-schedule their next follow-up visit and reinforce instructions to contact the study site to update locator information. Also, any difficulties experienced in contacting participants at these time points will serve to trigger timely mobilization of outreach efforts to ensure that participants are located in time for their next scheduled follow-up visit. The contacts may be conducted in-person at the study site, via telephone, or via street/home outreach.

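### Section 8.1 sends full DSMB review results to the local ethics boards and neither excludes nor defers interim results by arm

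*Protocol*

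**What the plan says.** Protocol Section 8.1 deals with reporting to the local ethics boards (IRBs/ECs), which it describes as "bodies responsible for oversight of research conducted at the study sites". It first sets the reporting cycle: "The investigator will make safety and progress reports to the IRBs/ECs at least annually and within three months of study termination or completion". It lists what those reports contain: enrolment, completion, changes to the research and unanticipated problems. The paragraph then ends: "In addition, all detailed results of DSMB reviews of the study will be provided to the IRBs/ECs".

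Protocol Section 7.6 describes what the DSMB reviews:

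- On frequency: "Primary and secondary endpoint data will be monitored annually".
- On whether arms are revealed: "The DSMB will be encouraged to conduct unblinded reviews of efficacy data".
- On how the arms become known to it: "At each interim efficacy analysis, the chairman of the DSMB will be given a sealed envelope with the randomization code enclosed".

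The same section places the code in the keeping of the biostatistician at the Statistical and Data Management Center (SDMC) and foresees sequential boundary guidelines for early termination. Section 6.1 adds that the DSMB routinely reviews social-harm data.

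Section 2.3 shields the behavioural assessments from knowledge of arm: "Behavioral risk survey interviewers will be blinded to the study arm of the participants". It also gives the time frame: "The study duration will be approximately 48 months".

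**The concern.** Interim comparative results are normally kept within the monitoring board and its statistician because people who learn of a trend may act on it. This trial has several places where that could matter. Facilitators know which indexes they train. Section 7.2.2 makes the risk-behaviour endpoints self-reported. Sections 4.1 and 7.3.4 recognise contamination between arms as a threat, and Section 3.6 makes retention depend on site effort. A known trend could alter how the intervention is delivered, how carefully contamination is limited or how hard each arm is followed up. Section 8.1 also has the local boards review the protocol at least annually. A board holding interim results by arm could weigh them without the sequential boundaries that guide the DSMB. Distortion of this kind is hard to detect or undo afterwards.

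**Working it through.** The protocol gives no figure to reproduce, because the point is who may see what, and when. The check sets Section 8.1 against Section 7.6 and then looks for any limiting text elsewhere.

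1. **Content of a DSMB review.** Sections 7.6 and 6.1 give three kinds of material: administrative data, social harms, and primary and secondary endpoint data. The code is supplied at each interim efficacy analysis and unblinded review is encouraged, so the third kind can include results by arm.

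2. **What is released.** Section 8.1 covers the results of DSMB reviews in full and in detail. It names no subset, and none of the three kinds is excluded.

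3. **Limits elsewhere.** Section 8.5 restricts release of participants' information, not of aggregate interim results. Section 10.6 governs publications. Section 7.6 says who holds the randomization code, but not who may see results produced with it. No section restricts interim comparative results.

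4. **Timing.** The release sentence carries no date. It closes a paragraph whose reports are due at least annually during the study, and nothing defers it to closure. Release during the trial is therefore the natural reading, though an inferred one.

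5. **Number of occasions.** With annual endpoint review over about 48 months, 48 / 12 = 4 annual time points. The last coincides with the planned end, which leaves 4 − 1 = 3 reviews before it. This assumes a first review at 12 months, and Section 7.6 gives no calendar. It counts possible review occasions, not disclosures by arm, and the earliest may hold few events.

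6. **Recipients.** The named recipients are the local boards. The sentence names no sender. The reports described just before it come from the investigator, so passage through site investigators is possible, but the text does not say so.

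**The case against.** The strongest reply is that Section 8.1 never mentions arms, efficacy or closed-session reports. Its sentence follows a description of safety and progress reports, and DSMB review also covers administrative matters and social harms. The authors may have meant only findings and recommendations. That is plausible, but the words chosen ask for everything in detail, so the reply supports rewording.

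Other parts of the reply stand, and they rule out stronger readings that a reader might infer:

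- *Results by arm will reach site staff every year.* Unblinded review is encouraged, not required. No sender or date is given, and no section has the boards pass results on.
- *Section 7.6 confines the code to the DSMB chair.* The SDMC biostatistician also holds it.
- *All site staff know assignment.* Facilitators necessarily do. The protocol does not say this of counsellors or outreach workers.
- *Every endpoint would be biased.* HIV infection is determined by a laboratory algorithm (Section 7.2.1), and the Central Laboratory retests seroconverters' specimens (Section 9.2). Only indirect effects, through delivery or retention, could touch it. For the behavioural endpoints, Section 5.3 requires the survey to be given by someone who is blinded and has not previously counselled the participant.
- *The stopping boundaries lose their error control.* Disclosure does not by itself change their error rate. Section 7.6 gives the boards no part in sequential monitoring, and Section 8.7 does not name them among those who may discontinue the study. The risk is only that a board might act on data read without the boundaries.

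**Conclusion.** The point holds as a defect in a rule that the protocol states outright. Followed literally, Section 8.1 permits interim HIV and behavioural results by arm to leave the DSMB during the trial, and no other section prevents it. The conclusion rests on two assumptions: that the DSMB takes up the unblinded review it is encouraged to make, and that release follows the annual reporting cycle. The effect on the trial's results cannot be sized from the document. The exposure could affect delivery, contamination control, retention or continuation decisions, but the protocol does not establish that it would. The sentence should be changed because the harm, if it occurred, could not readily be repaired, and the correction is small.

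**What to change.** Replace the last sentence of that paragraph in Section 8.1 with:

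> *After each DSMB review the IRBs/ECs will receive the DSMB's written summary and recommendation, including its findings on social harms and participant safety. Interim efficacy and behavioural results by arm will not be released outside the DSMB and the SDMC biostatistician holding the randomization code until the study closes, unless the DSMB recommends stopping or a change for participant safety. Detailed results will be provided after closure.*

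The restriction should go no further than this. Cutting the boards back to the bare fact of a review and its recommendation would deprive them of DSMB findings on social harms, a main participant risk in this study (Sections 6.0 and 8.3).

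The cost is that the boards see less comparative detail while the trial runs. They keep the enrolment, completion, change and unanticipated-problem reports already required by Section 8.1. The text change is short, but Section 10.4 requires approval by the Protocol Chair, the NIAID Program Officer, the IRBs/ECs and the DAIDS Regulatory Operations Center before it takes effect.
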